### **Overall Approach**

Analyses will be conducted using the latest version of the statistical software platform R and will be based on the intention-to-treat principle. All tests of significance will be two-sided and a p-value of 0.05 will be considered statistically significant. Summary statistics (e.g., mean, standard deviations, proportions) will be calculated for all variables of interest. Outliers will be assessed and variables whose distributions depart significantly from normality will be transformed. Appropriate non-parametric alternatives will be considered if parametric assumptions fail. No planned interim analyses for efficacy or futility will be conducted in this study.

- **Primary aim analysis:** The primary outcome of the study is change in objectively measured weight in kg, and the SMART 2.0 intervention groups will be compared to the control group using a mixed model of repeated measures (MMRM). The model will include change in weight from baseline at each post-baseline visit (i.e., 6, 12, 18, and 24 months) as the dependent variable. Fixed effects will include study group, visit, study group-by-visit interaction, weight at baseline, and any variables determined to be confounders. Visit will be treated as a categorical variable, and an unstructured variance-covariance structure will be used. Results will be reported as point estimates (mean differences between groups) and

interval estimates (95% confidence intervals). An intervention effect will be concluded if the p-value for the study group-by-visit interaction contrast in the model at 24 months is statistically significant. Holm's method will be used to adjust the two p-values for multiple comparisons. This approach uses all available data and is robust to data missing at random (MAR). However, two additional approaches may be employed to examine the influence of missing data on the primary outcome analysis (which takes a likelihood-based approach to estimation, but does not directly impute data). First, we will model the probability of missingness as a function of baseline covariates and previous outcomes (using logistic regression). The inverse of the resulting probabilities will serve as propensity scores that will be included in the model of the primary outcome. If data are MAR or the probability of missingness can be fully explained by observable data, this approach produces asymptotically unbiased estimates. Second, in order to allow for the possibility that the MAR assumption may not hold (an assumption that is not empirically testable), we will use pattern mixture models in which the distribution of the primary outcome is assumed to follow a mixture of two distributions: one for those who complete follow-up and another for those who do not. These approaches will allow us to quantify the robustness of the study findings to missing data assumptions.

- **Secondary aim analyses:** Secondary aim 1 will be achieved by using the MMRM approach outlined above to compare differences between the SMART 2.0 intervention groups and the control group at 6, 12, 18, and 24 months in anthropometric and physiological outcomes, PA, diet, sleep, body image, anxiety, depression, and the frequency and composition of participant's online communication about weight-related behaviors (all of these measures are continuous). Secondary aim 2 will examine the dose response (i.e., engagement with intervention modalities) of the SMART 2.0 interventions on outcomes at 6, 12, 18, and 24 months. Engagement variables will be included as independent variables in multiple regression models with the study outcomes as the dependent variable adjusting for covariates. Secondary aim 3 will examine the usability and acceptability of the intervention using the framework advanced by Strauss and Corbin. Transcribed audio recordings will be analyzed in three stages: open, axial, and selective coding. During open coding, the data will be examined line-by-line and key concepts and their properties will be discovered. Axial coding involves identifying the relationships among the data, which will then become fully integrated through selective coding. These processes will be documented via memos, which will provide a roadmap of the analytic process. Secondary aim 4 will be accomplished following methods outlined by MacKinnon and Kraemer. We will examine factors that may mediate or moderate the effect of the SMART 2.0 interventions on study outcomes. Mediators (e.g., PA, diet, social support) will inform how the intervention may have worked to change the outcome, while moderators (e.g., sex, age, social network connectivity, contamination) will illuminate for whom and under what conditions the intervention may have been efficacious. Mediation will be tested via path analysis with regression paths from randomized group to change in the mediator and from change in the mediator to change in the outcome, along with a direct path from the intervention to change in the outcome. Adding interaction terms to the models assessing the intervention effects will test moderation. Secondary aim 5 will examine patterns of PA, diet, and sleep as measured over 24 months by Fitbit and MyFitnessPal using Gaussian process regression models. Models will include separate long- and short-term trends for each of the intervention along with common terms for weekly and yearly periodic trends and indicator variables for holidays. We will also use the time-varying effect model to examine how changes in these behaviors over time influence weight. For all secondary analyses of interest, no adjustments for multiple comparisons will be made and a p-value of 0.05 will be considered statistically significant.

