## **Statistical Considerations**

### **Power and Sample Size**

In order to ensure that the RCT has adequate power to determine the efficacy of the SMART 2.0 intervention to improve weight in kg, we calculated the sample size based on a two-sided, two-sample t-test with 80% power at a significance level of 2.5% (a Bonferroni correction to account for two tests). In the SMART study, the standard deviation (SD) of change in weight at 6 and 12 months ranged from 3.87 kg to 5.97 kg, and we have assumed that the corresponding SD in SMART 2.0 will fall within this range. Furthermore, the smallest statistically significant mean difference in change in weight between the two groups occurred at 12 months and was approximately -1.33 kg. If we assume an SD of 4.92 and a modest increase in the between group difference (-1.60 kg), then we will need 182 subjects per group in order to detect a minimal standardized effect size of 0.33. Thus, we will randomize 642 participants (214 per group accounting for a 15% attrition rate).

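### The MMRM holds the baseline-weight slope constant over all four visits, and the plan does not say whether each aim 1 outcome's own baseline replaces baseline weight

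*Combined protocol and SAP*

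**What the plan says.** The primary analysis (section 8, Statistical Considerations, Overall Approach) is an MMRM for change in weight at the four post-baseline visits, with visit categorical and covariance unstructured. Its terms are given as: "Fixed effects will include study group, visit, study group-by-visit interaction, weight at baseline, and any variables determined to be confounders". Group is crossed with visit, while baseline weight enters as a main effect only. The efficacy conclusion rests on the 24-month contrast. The same paragraph says of the model: "This approach uses all available data and is robust to data missing at random (MAR". It then offers two optional missing-data sensitivity analyses, both for the primary outcome.

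For the secondary outcomes the plan states: "Secondary aim 1 will be achieved by using the MMRM approach outlined above to compare differences". This covers anthropometric and physiological measures, activity, diet, sleep, body image, mood and online communication, each tested at 0.05 without multiplicity adjustment. The text does not say which baseline covariate these models use. Table 7 schedules these groups of outcomes at month 0, so baseline values will exist.

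**The concern.** With change from baseline as the response, the slope on baseline need not be the same at every visit. If the correlation with baseline weakens over two years, the slope steepens, and a single slope adjusts the 24-month contrast with a value averaged over earlier visits. Dropout that depends on baseline is MAR, but a likelihood analysis corrects for it fully only if the mean model is right. Arm differences in retention are conceivable because contact differs greatly: 38 coaching sessions in T1 (26 in year one and 12 in year two), against devices alone in the control group.

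The second matter is ambiguity. Two analysts could fit different models to the same aim 1 outcome, one adjusting for baseline weight and one for the outcome's own baseline. For a noisy outcome the standard errors would differ noticeably.

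**Working it through.** **1. The plan's own figure.** The inputs are a difference of 1.60 kg, SD 4.92 kg, two-sided alpha 0.025 and 80% power (Power and Sample Size). d = 1.60/4.92 = 0.325. The normal approximation is n = 2(2.241 + 0.842)²/0.325² ≈ 180 per group. The t-based solution is 181.01, rounded up to 182, which agrees with "then we will need 182 subjects per group in order to detect a minimal standardized effect size of 0.33". Then 182/0.85 = 214.1, and 3 × 214 = 642. This calculation takes no credit for baseline adjustment, so the point below does not affect it.

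**2. When one slope is wrong.** The slope of change on baseline at visit t is rho_t × (SD_t/SD_0) − 1. With equal SDs, a correlation falling from 0.8 to 0.5 moves the slope from −0.2 to −0.5. With constant correlation and SDs the slope is constant and the single-slope model is correct. Bias at 24 months also requires baseline-related dropout that differs by arm, so that the retained groups differ in mean baseline.

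**3. Size for weight.** The documents give no baseline slopes, baseline SD or dropout model, so all of these are assumed. Two sets of simulations were run, both with a likelihood MMRM, unstructured covariance and roughly 15% missing at 24 months unless noted. Dropout depended on baseline weight differently by arm. Signs follow the direction assigned to dropout, so only sizes are shown.

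*Set A*: 3 × 214 participants, 450 replicates, change SDs 3.9, 4.9, 5.4 and 5.8 kg. Shown is the difference between single-slope and by-visit estimates.

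| Slopes per kg, over visits | Dropout log-odds per SD per visit | Difference |
|---|---|---|
| −0.045 to −0.10 | 0.25 | 0.04 kg |
| −0.045 to −0.10 | 0.5 | 0.08 kg |
| −0.03 to −0.045 | within 0.25 to 0.5 | 0.02 kg |
| dropout not arm-dependent | – | 0.00 kg |

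*Set B*: 400,000 subjects in two arms, true effect 0, baseline SD 14 kg, dropout in opposite directions by arm, SE rescaled to 214 per arm (about 0.61 kg). Monte Carlo error of the bias is about 0.02 kg.

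| Slopes per kg, over visits | Log-odds | Bias, one slope | Bias, by visit | Type I error, one slope (nominal 0.025) |
|---|---|---|---|---|
| constant −0.05 | 0.5 | 0.00 kg | 0.01 kg | 0.025 |
| −0.02 to −0.05 | 0.5 | 0.07 kg | 0.02 kg | 0.026 |
| 0 to −0.10 | 0.5 | 0.17 kg | 0.01 kg | 0.031 |
| 0 to −0.10 | 1.0 (19% missing) | 0.42 kg | 0.02 kg | 0.061 |

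With slopes 0 to −0.10 and dropout in the same direction in both arms, the bias was 0.01 kg. Under moderate inputs (log-odds up to 0.5) the range is therefore 0.02 to 0.17 kg, or 0.02/1.60 ≈ 1% to 0.17/1.60 ≈ 11% of the planned difference. At most this is 0.17/0.61 ≈ 0.28 of a standard error.

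**4. Single slope, secondary outcomes.** Here own baseline is in the model, the correlation falls from 0.8 to 0.5 over visits, and dropout is in opposite directions by arm. At log-odds 0.3 and 0.5 the bias was 0.023 and 0.037 SD, with type I error 0.057 and 0.068 against 0.05. At 1.0 it was 0.082 SD and 0.140. Adding own baseline by visit removed the bias to within Monte Carlo error (about 0.003 SD) and returned type I error to 0.050.

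**5. Precision, literal reading only.** With equal variances, a change score has variance 2(1 − rho) without own-baseline adjustment and 1 − rho² with it. The ratio is 2/(1 + rho).

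| Assumed rho | Variance ratio |
|---|---|
| 0.3 | 1.54 |
| 0.5 | 1.33 |
| 0.7 | 1.18 |
| 0.9 | 1.05 |

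At rho = 0.5, 182 per arm, alpha 0.05 and 80% power, the detectable difference is 0.294 SD without own baseline and 0.254 SD with it. Baseline weight is a weak substitute: if it correlates 0.3 with the outcome's baseline, the ratio at rho = 0.5 falls only from 1.33 to 1.30.

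**The case against.** The strongest objection concerns the aim 1 text. The plan says that the approach is reused, and the response must in any case change from weight to the new outcome. Replacing baseline weight by the new outcome's own baseline at the same time is the natural adaptation. This stands. A reader might infer that the secondary analyses as planned will lose precision across the board, but the documents do not support that. The loss arises only if baseline weight is kept, and even then it is slight for stable measures. What remains is an unstated choice.

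A reader might also infer that baseline weight is the only baseline adjustment. The same sentence admits further confounders, so it is only the one named baseline covariate. That clause has no list or selection rule, however, and provides no interaction with visit.

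A third inference would be that the stated robustness under MAR fails. That statement concerns the primary model, which already adjusts for its own baseline, and bias there needs both conditions in step 2. The documents give no evidence that heavier participants will leave one arm and lighter ones another: visit incentives do not differ by arm and every arm receives the devices. One baseline slope is also a common MMRM specification. The optional sensitivity analyses, one of which models missingness on baseline covariates and previous outcomes, give the primary outcome some further protection. The secondary outcomes have none.

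**Conclusion.** The point holds as a modest specification gap. The single slope can bias the 24-month weight contrast by about 0.02 to 0.17 kg under moderate assumed inputs, and a secondary contrast by about 0.02 to 0.04 SD. Both figures require a baseline slope that changes over visits and baseline-related dropout that differs by arm. With a constant slope, or with dropout that does not differ by arm, the bias is zero. The 0.42 kg case needs both the steepest slopes and the strongest dropout tried, and should not be read as expected.

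The aim 1 ambiguity costs precision only under the literal reading. Correlations, slopes, baseline SD and dropout strengths are all assumptions. The findings do not show that the primary conclusion is unsafe or that the trial is too small.

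**What to change.** In the primary model, replace the single baseline-weight term with baseline weight and its interaction with visit. In the aim 1 paragraph, add one sentence: each outcome's model adjusts for that outcome's own baseline value and that value's interaction with visit. Four visit-specific slopes in place of one cost 4 − 1 = 3 degrees of freedom per model. No new data are needed and the sample size does not change. The improvement is close to free and should be written in before unblinded data are analysed.

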Subjects assigned to the SMART 2.0 with technology and personal health coaching treatment group (T1) will receive the following during the 24-month (96 week) intervention period: 1) Fitbit Charge 3 activity tracker and Aria scale, 2) daily text messages related to physical activity, diet, sleep and weight loss/maintenance, 3) access to SMART 2.0 social media pages and content through an online group with 6 to 12 participants total, and 4) technology-mediated, real-time individual health coaching. Subjects will receive 1 to 2 text messages on a daily basis, be asked to use their Fitbit on a daily basis and self-weigh using the Aria at least once per week, be asked to interact with their online group via social media as frequently as possible, and speak with their health coach at a predetermined session schedule.

Subjects assigned to the SMART 2.0 technology alone treatment group (T2) will receive the following activities during the 24-month (96 week) intervention period: 1) Fitbit Charge 3 activity tracker and Aria scale, 2) daily text messages related to physical activity, diet, sleep, resilience and weight loss/maintenance, and 3) access to SMART 2.0 social media pages and content through an online group with 12 participants total.

Subjects will receive 1 to 2 text messages on a daily basis, be asked to use their Fitbit on a daily basis and self-weigh using the Aria at least once per week, and be asked to interact with their online group via social media as frequently as possible.

Subjects assigned to the control group will simply receive a Fitbit Charge 3 and Aria scale to use at their discretion.

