**Table 1. Examples of how intervention content will be delivered in SMART 2.0**

Content	Modalities	Description of Delivery
Intention formation and goal setting	Health coaching/ email, SMS, social media/ online groups	

- Health coach will facilitate long- and short-term goal setting with participant during each session followed by an email summary of goals made.

- Activity, dietary, and weight data collected by Fitbit and Aria scale will prompt tailored weekly goals disseminated via SMS.

- Health coach will moderate online group discussion so that each group develops and works toward goals. In turn, the health coach will post social media content tailored toward each groups' goals.

Self-monitoring	Fitbit, Aria scale, SMS, social media	

- Participant monitors physical activity, sleep, and diet with Fitbit and Fitbit app and weight with Aria scale. Ongoing self-monitoring is supported by prompts and reminders via SMS and social media.

Feedback	Health coaching, Fitbit/ Fitbit app, Aria scale, SMS,	

- Health coach will provide feedback on participant's progress toward reaching his/her individual goals.

- Feedback is provided in real time on devices and in Fitbit app.

	social media/online groups	
 
- A data driven automated SMS containing a summary of individual progress toward reaching tailored weekly goals is sent along with a message of encouragement or positive reinforcement.
 
- Participant posts about progress and/or challenges on social media and in online group and receives feedback from their social network, other participants and health coach.
 

Goal review	Health coaching, SMS	
 
- During health coaching sessions, participants will discuss goals and barriers and facilitators for achieving them.
 
- Automated SMS will be sent suggesting a new goal and providing feedback.
 

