### Online Group/ Social Media

After randomization, participants in T1 and T2 intervention-arms will be sorted by physical activity preference and placed in groups of 6 to 12 total participants through Facebook messenger. Current literature suggests that small, mixed-gender groups constructed based on a common characteristic (e.g. physical activity preference) result in improved outcomes in health interventions.

Each participant will “friend” the study health coach on Facebook, who will then add participants to their respective, private groups on Facebook Messenger. Content shared in the groups will only be accessible to the members of each group and the health coach. The health coach will post content and facilitate group discussion that follows a behavioral weight loss curriculum organized as a series of 24-week (6-month) cycles. Table 5 summarizes the content for the first 6-month cycle. Each subsequent cycle will follow the same format but will incorporate more advanced content and goals, dependent on group’s progress. Health coaches will also monitor all group interactions, respond to inquiries from participants, and elicit interactions using the following group-coaching methods:

1. *Mission statement formation:* Health coaches will work with group members at start of intervention (week 1) to establish ground rules and roles for participants and health coach. This mission statement will be revisited every 6-months and revised as necessary.
2. *Informational content and resources:* Health coaches will provide relevant informational content and resources applicable to the weekly curriculum topic as well as the group’s interests, recommendations

and goals. This includes, but is not limited to, local bike/running maps, healthy eating options on or near campus, recipes and exercise routines.

3. *Knowledge check-ins*: Health coaches will frequently assess group knowledge of weekly curriculum topics through polls and Q&A's. The intent is to give participants an opportunity to ask the health coaches questions relevant to weight loss and health behaviors.
4. *Shared experiences*: To elicit group cohesion and social support, health coaches will present open-ended questions designed to encourage participants to share their experiences with adopting and maintaining health behaviors and reaching personal weight loss goals. For example, a health coach may ask the group to share their favorite on-the-go healthy snack option.

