## **Comparison Condition**

The comparison condition will also receive a Fitbit Charge 3 and Aria Scale to use at their discretion. This will allow participants to access the Fitbit smartphone application which includes physical activity, dietary and sleep tracking.

The study is implementing mechanisms for preventing comparison group subjects from accessing the intervention components of the SMART 2.0 study. For example, tailored content, goal and behavior feedback, and participant-to-participant and participant-to-health coach interactions will be reserved only for private, invitation-only online groups for participants in the two treatment groups.

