## **10. RECRUITMENT AND PROCEDURES PREPARATORY TO RESEARCH**

We will develop an enrollment strategy to ensure that we enroll students, faculty and staff across the broad age-range targeted in this initiative (18-35 years). Subjects will be recruited from three college and university settings within San Diego County including: UCSD, SDSU and CSUSM.

Participants will be recruited through the following channels: (1) digital advertisements in college e-newsletters; (2) targeted social media advertisements; (3) posting of print and digital flyers at UCSD and CSUSM; (4) e-mails sent by student health services via electronic distribution lists and by departmental listserv managers; (5) campus-wide events via tabling.

Interested individuals will be directed to complete an online screening form through the study's secure REDcap database. Once the subject arrives at the screening form, he/she will have an opportunity to read and learn more about the study. At this point, the subject will be explained that in order to determine whether he/she meets the criteria for participating, he/she will be asked a few eligibility questions (see eligibility criteria described above). After the participant completes the form, study staff will follow up accordingly. Participants who do not

meet the eligibility requirements will receive an email notifying them and thanking them for their interest in the study. Participants who meet the eligibility requirements will receive a call from a trained research staff notifying them that they qualify, informing them about the study purpose, procedures, risks and benefits, explaining that they may be randomized to a control condition that includes a Fitbit Charge 3 and Aria Scale, and to confirm information provided in the online screening form. Once this is complete and the subject still qualified, he/she will be invited to schedule an appointment at the research office. There they will be re-screened for inclusion and exclusion criteria, provide written informed consent, and complete the baseline measurement. After eligibility and consent are confirmed and baseline measurements are completed, participants randomized at a ratio of 1:1:1. The biostatistics team will generate the electronic randomization list using the latest version of the statistical software platform R (currently version 3.3.2, <http://www.r-project.org>)

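### T1 and T2 are treated in interacting online groups and controls are not, but the sample size and primary MMRM assume independent participants; positive within-group correlation would make the Holm tests liberal

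*Combined protocol and SAP*

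**What the plan says.** All references are to the combined protocol and SAP.

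- **Randomization.** Section 10 allocates individuals: "participants randomized at a ratio of 1:1:1".
- **Grouping after randomization.** Under Online Group/ Social Media, "participants in T1 and T2 intervention-arms will be sorted by physical activity preference and placed in groups of 6 to 12 total participants". The Overview in section 8 describes T1 as having an "online group with 6 to 12 participants total" and T2 as having "access to SMART 2.0 social media pages and content through an online group with 12 participants total".
- **Group-level treatment.** Table 1 states: "Health coach will moderate online group discussion so that each group develops and works toward goals". The curriculum also adapts to each group's progress: "Each subsequent cycle will follow the same format but will incorporate more advanced content and goals, dependent on group".
- **Controls.** They receive the devices only. Under Comparison Condition, "participant-to-participant and participant-to-health coach interactions will be reserved only for private, invitation-only online groups for participants in the two treatment groups".
- **Sample size.** Power and Sample Size uses a two-sided two-sample t-test at 2.5% with 80% power, SD 4.92 kg and a difference of -1.60 kg. This gives 182 per arm, and 214 per arm (642 in total) after 15% attrition.
- **Primary analysis.** Overall Approach specifies an MMRM with arm, visit, arm-by-visit, baseline weight and any confounders. On covariance it says only: "Visit will be treated as a categorical variable, and an unstructured variance-covariance structure will be used". Holm's method is applied to the two 24-month contrasts. The additional analyses of the primary outcome concern missing data.

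**The concern.** The design is partially nested: treated participants share a small interacting group for 24 months, and controls do not. An unstructured matrix over visits is a sound choice for repeated measures on one person, but it says nothing about two people in the same group. Statistical Considerations contains no online-group term, cluster-robust variance, ICC or design effect.

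On the protocol's own reasoning, the groups are meant to influence members jointly, through cohesion, social support and shared goals. Positive correlation is therefore plausible, though not established. If it exists, the T1-control and T2-control comparisons overstate their precision, and the trial's primary claim carries more false-positive risk than planned. Secondary aim 1 reuses the same model. Network connectivity and contamination appear only as moderators under secondary aim 4, which does not correct a standard error.

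**Working it through.** **Reproducing the plan.** The exact noncentral-t calculation with difference 1.60, SD 4.92, two-sided 2.5% and 80% power gives 182 per arm (power 80.2%). Then 182/0.85 = 214.1, which the plan takes as 214, and 3 × 214 = 642. The stated figures follow under independence, with no allowance for clustering.

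**Inputs.**
- From the plan: 182 analysed per arm, 15% attrition, groups of 6 or 12.
- Analysed members per group, m: 6 × 0.85 = 5.1 and 12 × 0.85 = 10.2.
- Assumed: ICC of 0.01, 0.02, 0.05 or 0.10, and groups formed within arm.

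**Formulas.** Only the treated arm is clustered.
- Design effect in the treated arm: DE = 1 + (m − 1) × ICC.
- True over naive standard error of a contrast: k = √((1 + DE)/2).
- Critical value z = 2.2414. Noncentrality = 1.60/(4.92 × √(2/182)) = 3.102.
- Actual per-comparison error of the planned test: 2 × (1 − Φ(z/k)).
- Power of a group-adjusted test, large sample: Φ(3.102/k − z).
- Family-wise error: under the global null, Holm rejects at least once when the smaller p-value is at most 0.025. This is 1 − P(|z1| < z and |z2| < z), with z1 and z2 bivariate normal, variance k² and covariance 0.5 from the shared control arm.

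**One case in full (groups of 12, ICC 0.05).** DE = 1 + 9.2 × 0.05 = 1.46. k = √1.23 = 1.109. Per-comparison error = 2 × (1 − Φ(2.021)) = 4.3%, against 2.5%. Group-adjusted power = Φ(2.797 − 2.241) = 71.1%. Coverage of a nominal 95% interval = 2Φ(1.960/1.109) − 1 = 92.3%.

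**Results.**

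| Assumed ICC | Family-wise error, groups of 6 | Family-wise error, groups of 12 | Group-adjusted power, groups of 6 | Group-adjusted power, groups of 12 |
|---|---|---|---|---|
| 0 | 4.65% | 4.65% | 80.5% | 80.5% |
| 0.01 | 4.9% | 5.3% | 79.7% | 78.6% |
| 0.02 | 5.2% | 6.0% | 78.8% | 76.6% |
| 0.05 | 6.1% | 8.1% | 76.2% | 71.1% |
| 0.10 | 7.7% | 11.9% | 72.1% | 62.8% |

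**Sensitivity at ICC 0.05.**
- With full assigned group sizes (no attrition within groups), family-wise error is 6.5% (groups of 6) or 8.8% (groups of 12), and group-adjusted power is 75.3% or 69.4%. These are upper values for the error. The MMRM uses partial data from people who drop out, so the truth lies between the two sets.
- If groups mixed T1 and T2 evenly, m/2 members per arm would share a group. Then DE = 1 + (m/2 − 1) × ICC and the covariance is 0.5 + (m/2) × ICC/2. At full assigned sizes, family-wise error falls from 6.5% or 8.8% to 5.2% or 6.2%.

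All figures approximate a single time point and ignore baseline adjustment.

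**The case against.** **No ICC is given.** Nothing in the documents supports 0.05 or 0.10 over 0.01. Several features limit differences between groups: standardized content, fidelity checks on coaches, individually tailored texts and individual coaching in T1. At ICC 0.01 with groups of 6, family-wise error stays below 5%. This stands, and it is why the point is conditional.

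**The nesting is not clean.** The Online Group/ Social Media section lets participants communicate through posts on the shared study pages. Engagement with Intervention Modalities expects controls to be connected to, and interact with, intervention participants. Positive treated-control correlation would reduce the variance of a contrast and offset some of the inflation. This stands as a limit on both the illustration and the fix.

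**Within-arm grouping is not stated.** The different T1 and T2 sizes in the Overview suggest it, but do not settle it. Mixed groups would make the problem smaller.

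**A cluster correction can overshoot.** Groups are sorted by activity preference. If preference predicts weight change and is not adjusted for, the corrected test can be conservative. In a simulation with 15 groups of 12 and ICC 0, its error was 1.1% or 0.5%, against a nominal 2.5%, when preference explained 5% or 10% of outcome variance. Activity preference is not among the listed measures, and the text on DXA scan speeds suggests that enrolment may have begun. This stands, so preference adjustment should not be mandatory.

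**Stronger readings to avoid.** A reader might infer that the trial's error rate is known to be inflated, that sorting by preference itself inflates the variance, or that 642 is too few. The first and third need an ICC the documents do not supply. The second is wrong: sorting people who are already randomized does not by itself change the variance of an arm mean. Outcome correlation created by shared treatment does.

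**Conclusion.** The point holds conditionally. Treatment is delivered in interacting groups in two arms only, and the plan assumes independence without saying so. If within-group correlation is positive and not offset by treated-control ties, the standard errors are understated and the Holm tests are liberal. For assumed ICCs of 0.01 to 0.10, within-arm groups and 15% attrition, family-wise error runs from 4.9% to 7.7% (groups of 6) or 5.3% to 11.9% (groups of 12). The power of a test that accounts for groups runs from 79.7% to 72.1%, or from 78.6% to 62.8%. The true ICC is unknown, and the effect is negligible at the low end. The unstructured covariance over visits is not itself at fault. This should be fixed in the SAP, but it does not show that the design fails.

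**What to change.** 1. Store each participant's assigned online group as an analysis variable. The planned tracking of study-engineered network connections may already supply it.
2. Reconcile the group sizes in the Overview with those under Online Group/ Social Media, and state whether groups are formed within arm.
3. Prespecify one method that accounts for online group in the primary MMRM and the analyses that reuse it. Two are suitable: cluster-robust standard errors with a small-sample correction and each control as a singleton, or a partially nested model with a group random effect in T1 and T2 only and small-sample degrees of freedom.
4. Adjust for activity preference only if it is available before randomization in all three arms. Otherwise state that the cluster-adjusted test may be conservative.
5. Restate power at 642 over a stated ICC range.
6. State as limitations that clustering by health coach, interaction on shared study pages and treated-control ties are not covered.

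**Cost.** SAP wording, some R code and a stored group identifier, with no added enrolment. Intervals would be somewhat wider and the stated power less favourable. If the ICC is 0 there is still a small loss: with cluster-robust (CR2) standard errors and Satterthwaite degrees of freedom, simulated power fell from 79.8% to 79.0% (groups of 6) and from 79.6% to 77.7% (groups of 12). That simulation used 180 per arm, full group sizes and one time point. It has not been repeated for the four-visit model with missing data.
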